interrupted dose at a slower infusion rate (half of the rate at which hypersensitivity reaction occurred) pending all signs and symptoms of hypersensitivity have resolved. If a \geq Grade 3 hypersensitivity reaction is observed, the TPI 287 infusion will be stopped and appropriate supportive care administered until the symptoms resolve. The subject will be discontinued from the trial.

Dose Definition

Dose Escalation Phase:

The starting dose (i.e., dose level 1) will be 14 mg/m^2 /dose. Provided that MTD has not been reached, the TPI 287 dose will be increased as follows:

Dose Escalation Schedule		
Dose Level	Dose	
	TPI 287 IV	Radiotherapy
Level -2	5 mg/m ² /dose	5 Gy daily fraction
Level -1	7 mg/m ² /dose	5 Gy daily fraction
Level 1	14 mg/m ² /dose	5 Gy daily fraction
Level 2	28 mg/m ² /dose	5 Gy daily fraction
Level 3	56 mg/m ² /dose	5 Gy daily fraction
Level 4	85 mg/m ² /dose	5 Gy daily fraction
Level 5	113 mg/m ² /dose	5 Gy daily fraction
Level 6	$127.5 \text{ mg/m}^2/\text{dose}$	5 Gy daily fraction

Table 1. Dose Escalation Schedule

If dose level 1 is found to cause unacceptable toxicity, the dose will be de-escalated to levels -1 or -2.

Dose Expansion Phase:

The TPI 287 dose used in the dose expansion cohort will be MTD determined from the dose escalation phase. TPI 287 will be administered intravenously prior to treatment of brain metastasis with FSRT on day 1 and will be given for 2 more weekly doses. The prescription dose of FSRT will be 25 Gy in 5 daily fractions as described in section 5.2.

Definition of Maximum Tolerated Dose:

The maximum tolerated dose (MTD) is the highest dose of TPI 287 that does not cause unacceptable toxicity in more than one of six patients at that dose level. The MTD is defined as one dose level below the highest toxic dose (i.e., the DLT dose).

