Number of Patients with DLT at a Given Dose Level	Escalation Decision Rule
0 out of 3	Enter 3 patients at the next dose level.
≥2	Dose escalation will be stopped. This dose level will be declared the maximally administered dose (highest dose administered). Three (3) additional patients will be entered at the next lowest dose level if only 3 patients were treated previously at that dose.
1 out of 3 or ≥ 2 grade 2 CNS toxicities	 Enter at least 3 more patients at this dose level. If 0 of these 3 patients experience DLT, proceed to the next dose level. If 1 or more of this group suffer DLT, then dose escalation is stopped, and this dose is declared the maximally administered dose. Three (3) additional patients will be entered at the next lowest dose level if only 3 patients were treated previously at that dose.
≤1 out of 6 at highest dose level below the maximally administered dose	This is the dose to be used in the expanded cohort and will be considered recommended phase 2 dose. At least 6 patients must be entered at this dose.

Table 2. Dose Escalation Rules

If dose level 1 is found to cause unacceptable toxicity, the dose will be de-escalated to level -1 (7 mg/m^2). Three patients will be enrolled at dose level -1. If no DLT is observed, three additional patients will be enrolled at dose level -1 such that safety is established in at least 6 patients prior to entering dose expansion phase.

Any delayed CNS-toxicity arising within the radiation field but seen beyond the window for DLT registration (> 8weeks following completion of FSRT) will be recorded. Furthermore, occurrence of any delayed-onset treatment related grade 3 or higher central nervous toxicity at any time (during and after DLT period of 8 weeks) will lead to holding dose-escalation and adding 3 patients to the dose level at which toxicity has occurred. Occurrence of additional delayed-onset treatment related grade 3 or higher CNS- toxicity will be reviewed with Protocol Monitoring Committee and IRB to determine whether discontinuation or modification of trial is subsequently warranted.

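### Table 2 and section 5.3 select different doses for one 1-in-6 outcome, and no rule closes out the top level when it is cleared on three patients

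*Combined protocol and SAP*

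**What the plan says.** Section 5.3 defines the MTD twice. Sentence 1 makes it the highest dose that "does not cause unacceptable toxicity in more than one of six patients at that dose level". Sentence 2 reads: "The MTD is defined as one dose level below the highest toxic dose (i.e., the DLT dose"). The same section fixes what follows: "The TPI 287 dose used in the dose expansion cohort will be MTD determined from the dose escalation phase".

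Table 2 in section 5.4 gives the escalation rules.

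- After 0/3 DLTs: "Enter 3 patients at the next dose level".
- The expansion row is headed "1 out of 3 or ≥ 2 grade 2 CNS toxicities". It adds at least three patients. With no DLT among three added patients, escalation continues. Otherwise: "If 1 or more of this group suffer DLT, then dose escalation is stopped, and this dose is declared the maximally administered dose".
- When escalation stops, the level below receives three more patients if it had only three.
- The last row covers "≤1 out of 6 at highest dose level below the maximally administered dose" and says: "This is the dose to be used in the expanded cohort and will be considered recommended phase 2 dose". It requires at least six patients at that dose.

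The text after Table 2 spells out how level -1 is filled from three to six patients before expansion. Section 14.2 sets a maximum of 36 patients for escalation and 10 in the expansion phase, counting those already treated at the MTD.

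**The concern.** The MTD is a primary endpoint and fixes the expansion dose, so each outcome the rules allow should lead to one dose. Two outcomes do not.

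1. **Expansion on the CNS trigger alone, then one DLT.** The level has 1/6. Table 2 stops and looks one level lower; sentence 1 of 5.3 accepts the level. Two people following the text on the same data would expand at 56 or 85 mg/m² (stop at level 4), 28 or 56 (level 3), or 7 or 14 (level 1).
2. **0/3 at level 6.** The instruction is to go to a next level, and level 6 is the last. The recommended-dose row needs a maximally administered dose, and none has been declared. Nothing instructs the site to treat three more patients at 127.5 mg/m² before expansion.

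A smaller point is that sentence 2 of 5.3, taken alone, names the level below the stopped dose even when the added patients bring that level to 2/6 or more.

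**Working it through.** **The plan's own figure.** Six ascending levels with six patients each give 6 × 6 = 36, which matches section 14.2.

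**Tracing the rules**

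| Outcome | Table 2 | 5.3 sentence 1 | 5.3 sentence 2 |
|---|---|---|---|
| 1/3, then at least 1 of 3 (2/6 or more) | stop, go lower | not the MTD | level below |
| 0/3 with CNS trigger, then 1 of 3 (1/6) | stop, go lower | acceptable as MTD | level below, only if the DLT dose means the stopped dose |
| Level below brought to 2/6 or more | fails last row | not the MTD | read alone, still names it |
| Level 6 at 0/3 | next level (none exists) | cannot apply: three treated | no toxic dose exists |
| Level 6 cleared on six patients | next level (none exists) | level 6 is the MTD | no toxic dose exists |

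The first row is the ordinary 3+3 path and is not in dispute. The group in the stop rule must be the added patients; otherwise a trigger of 1/3 would always stop the trial.

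**How often.** The documents give neither DLT nor grade 2 CNS rates, so all rates here are assumptions. Let p be the DLT rate at a level, q = 1 − p, and g the proportion of patients with a grade 2 CNS toxicity, independent of DLT. Counting patients, the CNS trigger has probability t = 3g²(1 − g) + g³, which is 0.104 at g = 0.2 and 0.352 at g = 0.4. Per level:

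- advance on three: a3 = q³(1 − t)
- advance on six: a6 = (q³t + 3pq²)q³
- case 1 stop: c = q³t × 3pq²

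With R_k the product of (a3 + a6) over levels below k, case 1 has probability Σ R_k c_k, and level 6 cleared on 0/3 has probability R_6 × a3 at level 6.

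Worked example, p = 10% at every level, g = 0.2:

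- q³ = 0.729, so a3 = 0.729 × 0.896 = 0.6532
- a6 = (0.729 × 0.104 + 0.243) × 0.729 = 0.2324
- a3 + a6 = 0.8856
- c = 0.729 × 0.104 × 0.243 = 0.01842
- Case 1: 0.01842 × (1 + 0.8856 + 0.7843 + 0.6946 + 0.6151 + 0.5447) = 0.0833, or 8.3%
- Level 6 on 0/3: 0.5447 × 0.6532 = 0.356, or 35.6%

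The rising curves over levels 1 to 6 are A (2, 3, 5, 8, 12, 17%), B (2, 4, 7, 12, 20, 30%) and C (5, 10, 15, 25, 35, 50%). Results are percentages of trials:

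| | flat 10% | A | B | C |
|---|---|---|---|---|
| Case 1, g = 0 | 0 | 0 | 0 | 0 |
| Case 1, g = 0.2 | 8.3 | 7.3 | 7.2 | 6.5 |
| Case 1, g = 0.4 | 25.1 | 22.7 | 22.3 | 20.3 |
| Level 6 on 0/3, g = 0.2 | 35.6 | 37.3 | 16.0 | 1.6 |
| Level 6 on 0/3, g = 0.4 | 19.4 | 22.5 | 9.1 | 0.8 |
| Lower level fails after added patients, g = 0.2 | 0.8 | 0.8 | 2.8 | 6.4 |

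Table 2 does not say whether the CNS trigger counts patients or events. If events are counted (Poisson, mean −3 ln(1 − g) for three patients), t becomes 0.145 and 0.453, and case 1 at a flat 10% rises to 11.4% and 30.8%. The model leaves out the extra patients that 5.4 adds after delayed grade 3 or higher CNS toxicity.

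**The case against.** **Table 2 governs.** Section 5.4 makes the table the operative escalation scheme, and sentence 2 of 5.3 can be read to agree with it, so only sentence 1 dissents. Sentence 1 also speaks of unacceptable toxicity, not DLT. This narrows case 1 without removing it: 5.3 and the last row of Table 2 each fix the expansion dose, unacceptable toxicity has no separate definition, and the stricter CNS trigger is this protocol's own addition, so calling the design a standard 3+3 does not settle the outcome.

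**A failed lower level.** A reader might infer that the plan sends the expansion to a dose with 2/6 or more DLTs. The documents do not support that. Sentence 1 and the last row of Table 2 both reject such a level, so sentence 2 is a drafting slip.

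**Three or six at the top.** A reader might infer that three patients could suffice at 127.5 mg/m². They could not: Table 2 requires six at the recommended dose, sentence 1 counts out of six, and the 36 leaves room for six at level 6. What is missing is the row that applies this. If level 6 is cleared on six patients, sentence 1 names it the MTD, so only the 0/3 frequencies are relevant.

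**Assumed rates.** Case 1 disappears without grade 2 CNS toxicity. Section 7.1.1 lists headache as an expected early radiation effect, which makes the trigger plausible but does not establish its rate. Level 6 equals the weekly single-agent MTD (section 2.2), so low DLT rates up to that level, which favour the second gap, may be optimistic.

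**Conclusion.** The concern holds for two outcomes. With 1/6 after an expansion opened only by the CNS trigger, Table 2 and sentence 1 of 5.3 choose different doses. With 0/3 at level 6, the rules yield no dose and no instruction to reach six patients. The wording of sentence 2 is a minor third point.

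Over the four assumed DLT curves, case 1 occurs in 6.5 to 8.3% of trials at a 20% grade 2 CNS rate, in 20.3 to 25.1% at 40%, and never at 0%. Level 6 is cleared on 0/3 in 1.6 to 37.3% at 20%. These figures assume the CNS trigger counts patients and is independent of DLT. The two textual gaps do not depend on the rates; only their frequency does. The point should be fixed because it concerns the primary endpoint and the remedy is cheap. It does not show that the plan would select an unsafe dose.

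**What to change.** (a) Delete sentence 2 of the MTD definition in 5.3. Define the MTD and recommended phase 2 dose as the highest level with at least six evaluable patients, at most one DLT in six, and no declaration as the maximally administered dose. This keeps the stricter CNS stop. For levels with more than six patients, state the limit, for example an observed DLT proportion no higher than 1/6; with nine patients that allows one DLT (1/9 = 11.1%) but not two (2/9 = 22.2%).

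(b) If a level that received added patients has two or more DLTs, treat it as above the MTD, step down, fill the next lower level to six and apply the same limit.

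(c) Add a Table 2 row: after 0/3 at level 6 without the CNS trigger, enter three more patients and complete their 8-week DLT window before expansion. If at most 1/6 have a DLT, 127.5 mg/m² is the MTD and recommended dose; otherwise fill level 5 to six and apply the same limit. If level 6 is expanded under the existing row and none of the added three has a DLT, 127.5 mg/m² is the MTD and recommended dose.

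(d) State whether the CNS trigger counts patients or events.

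**Cost.** Wording; up to three patients at level 6, who count toward the 10 only if level 6 becomes the MTD; one more DLT observation period before expansion; and occasional step-down patients. The maximum of 36 for levels 1 to 6 is unchanged. At a true 30% DLT rate, ignoring the CNS trigger, the unconditional chance that level 6 starts with 0/3 and is accepted falls from 0.7³ = 34.3% to 0.343 × (1 − 0.216) = 26.9%, where 0.216 is the chance of at least two DLTs among the added three. Given a 0/3 start, acceptance falls from 100% to 78.4%.

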5.4 Definition of Dose-Limiting Toxicity

Toxicities will be graded in severity according to the guidelines outlined in the NCI-CTCAE version 4.0. Dose limiting CNS and non-CNS (hematologic and non-hematologic) toxicities will be defined differently and will be based on events that occur during the study period. In order to be declared as dose-limiting toxicity, an adverse event must be related (definite, probable, or possible) to study treatment.

A dose-limiting toxicity (DLT) will be defined as any one of the following adverse events occurring within 8 weeks from last dose of radiation therapy:

CNS toxicities:

Acute CNS toxicities (occurring \leq 30 days after completing FSRT treatment):

• Any grade 3 or higher central nervous adverse events including but not limited to headache, dizziness, vertigo, new onset seizures, cerebral edema, cerebral hemorrhage, and new onset neurologic deficit.

Delayed onset CNS toxicities (occurring >30 days after completing FSRT treatment):

 Any grade 3 or 4 adverse event arising within the irradiated volume including but not limited to radiation necrosis or focal neurological deficits.

Non-CNS toxicities:

Non-hematologic toxicities:

- Any grade 3 or higher non-hematologic adverse event with the exception of alopecia, fatigue, and anorexia.
- Grade 3 or higher nausea and/or vomiting that persists ≥ 48 hours despite optimal medical management.

Hematologic toxicities:

- Grade 4 neutropenia lasting for \geq 7 days in duration
- Grade \geq 3 febrile neutropenia with/without infection

• Grade 4 thrombocytopenia

Dose escalation will be determined based on the occurrence of DLTs. For the purposes of determining whether to advance the dose levels, DLTs will be counted by patient. In the event of the development of any grade 3 or 4 toxicity felt to be at least possibly related to study drug, TPI 287 will be held until resolution to grade 1 or baseline assuming that occurs within 15 day window.

Dose escalation will follow the standard 3+3 design. The enrollment to next higher dose level will be delayed for 8 weeks after the completion of FSRT by the last patient enrolled at the dose level. This period of 8 weeks will allow monitoring potential delayed toxicities. Management and dose modifications associated with the above adverse events are outlined in Section 6. Dose escalation will proceed according to the following scheme. Dose-limiting toxicity (DLT) is defined above.

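### Once level 1 is found too toxic, sections 5.3 and 5.4 do not give one consistent decision for every outcome at levels -1 and -2

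*Combined protocol and SAP*

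**What the plan says.** Section 5.3 sets the start at level 1 (14 mg/m² per dose) and lists two lower levels, -1 (7 mg/m²) and -2 (5 mg/m²). If level 1 is too toxic, "the dose will be de-escalated to levels -1 or -2". It then defines the MTD in two sentences. The first is the highest dose with unacceptable toxicity in no more than one of six patients. The second is one level below the highest toxic dose.

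Section 5.4 states that "Dose escalation will follow the standard 3+3 design" and gives four rows in Table 2, written for any dose level:

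- Row 1, 0 of 3: go to the next level.
- Row 2, two or more DLTs: stop escalation and declare this level the maximally administered dose. Three more patients enter the level below if exactly three were already treated there.
- Row 3, 1 of 3 (or at least two grade 2 CNS toxicities): add at least three patients. "If 0 of these 3 patients experience DLT, proceed to the next dose level". With one or more further DLTs, stop and step down on the same condition as in row 2.
- Row 4, at most 1 of 6 at the highest level below the maximally administered dose: this is the expansion dose and the recommended phase 2 dose.

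The paragraph after Table 2 deals with failure of level 1: "If dose level 1 is found to cause unacceptable toxicity, the dose will be de-escalated to level -1". Three patients are enrolled there. "If no DLT is observed, three additional patients will be enrolled at dose level -1", so that six have been treated before expansion. The paragraph does not mention level -2.

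**The concern.** The primary objective is the MTD, and the expansion cohort is treated at it. If level 1 fails, staff need a rule for each possible count of DLTs at level -1 and, if that level fails too, at level -2. The paragraph after Table 2 supplies one for a single outcome. Table 2 was drafted for moving upward from level 1, and below level 1 its wording partly contradicts itself or cannot be applied. The decisions left open are those taken just after a level has been found too toxic. The risk is an improvised decision, or two readers of the same protocol declaring different expansion doses.

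The branch is not far-fetched. Under section 5.4 a DLT need only be possibly related to study treatment, and the full 25 Gy of FSRT is given at every drug level. Grade 3 or higher acute CNS events such as headache, seizure or edema count, in patients who have brain metastases.

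**Working it through.** **The plan's own figure.** Section 14.2 caps escalation at 36. Levels 1 to 6 at six patients each give 6 × 6 = 36, so the figure reproduces. All eight levels would give 8 × 6 = 48. The path 1, -1, -2 uses at most 3 × 6 = 18, so the cap is not at issue.

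**Outcomes at level -1 after level 1 has failed.**

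| Outcome at -1 | Paragraph after Table 2 | Table 2 |
|---|---|---|
| 0/3 | three more at -1 | row 1 says next level; the specific paragraph displaces it |
| 0/3 then at most 1/3 | six treated, then expansion | row 4: expansion dose |
| 0/3 then 2 or 3 of 3 | silent | row 2: step down, condition not met |
| 1/3 then 0/3 | silent | row 3: next level (level 1); row 4: expansion dose |
| 1/3 then at least 1/3 | silent | row 3: step down, condition not met |
| 2 or 3 of 3 | silent | row 2: step down, condition not met |

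The step-down condition requires three patients already treated at the lower level. Coming down from -1, nobody has been treated at -2, so the clause enters no one. Row 2 would also label level -1 the highest dose administered, although level 1 was given.

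**The two MTD sentences.** Suppose levels 1 and -1 both fail. The highest toxic dose, read literally, is level 1, and one level below it is -1. The first MTD sentence rules out -1, because more than one of six had unacceptable toxicity there.

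**How often this arises.** The documents give no DLT rate, so assume the same rate p at levels 1 and -1, with independent patients. Let a = (1-p)³, the chance of 0/3; b = 3p(1-p)², of 1/3; and c = 1-a-b, of 2 or 3 of 3.

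- Level 1 fails: F = 1 - a - ab
- At least one DLT in the first three at -1 (paragraph silent): F × (1-a)
- Row 3 against row 4 (1/3 then 0/3): F × ab
- Level -1 fails, so a rule for -2 is needed: F × [c + b(1-a) + ac]

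| p | a | b | c | F | silent after first 3 | row 3 v row 4 | rule for -2 needed |
|---|---|---|---|---|---|---|---|
| 0.10 | 0.729 | 0.243 | 0.028 | 0.094 | 0.094 × 0.271 = 2.5% | 0.094 × 0.177 = 1.7% | 0.094 × 0.114 = 1.1% |
| 0.15 | 0.614 | 0.325 | 0.061 | 0.186 | 0.186 × 0.386 = 7.2% | 0.186 × 0.200 = 3.7% | 0.186 × 0.224 = 4.2% |
| 0.20 | 0.512 | 0.384 | 0.104 | 0.291 | 0.291 × 0.488 = 14.2% | 0.291 × 0.197 = 5.7% | 0.291 × 0.345 = 10.0% |

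The last three columns overlap and must not be added together. F is sensitive to p: 2.7% at 0.05 and 50.6% at 0.30. The calculation leaves out cohorts expanded for grade 2 CNS toxicity alone. It also leaves out a later failure of level 1 when it is expanded after level 2 has failed.

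**The case against.** A reader might infer that Table 2 sends a cleared cohort at level -1 back up to the level just rejected. The documents do not support that. For 0 of 3, the paragraph after Table 2 keeps the cohort at -1 and leads to expansion. For 1 of 3 then 0 of 3, escalation has already been stopped at level 1, row 4 fits the result exactly, and section 5.3 makes dose increases conditional on the MTD not having been reached. Staying at -1 is therefore the more natural reading. What stands is that row 3 says the opposite in plain words and nothing states that row 4 overrides it.

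A reader might also infer that there is no route to level -2 at all. That goes too far: section 5.3 names it, and rows 2 and 3 refer to the level below, which from -1 is -2. What stands is that the condition attached to that step cannot be satisfied, and nothing says what to do after an outcome at -2.

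Finally, the starting dose is about one ninth of the weekly single-agent MTD reported in section 2.2 (127.5/14 = 9.1), so the branch may never be reached. That is a fair reason to keep the point in proportion. It does not remove it, because toxicity possibly related to FSRT does not fall with the drug dose.

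**Conclusion.** The point holds as an inconsistency in the rules below level 1, with four parts: a paragraph that covers only 0 DLTs in 3 at level -1; a conflict between rows 3 and 4 of Table 2 for 1 of 3 then 0 of 3; no operable entry rule for level -2; and two MTD sentences that can disagree if levels 1 and -1 both fail. It does not show that the plan re-exposes patients at a rejected dose.

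The textual findings need no assumption. The frequencies in the working do: they rest on an assumed common DLT rate of 10-20% and independent patients. On that basis the affected branches are uncommon but not negligible. The matter should be corrected, because it concerns the primary endpoint and the decision that follows a toxic cohort.

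**What to change.** Reconcile rows 2 to 4 of Table 2, the paragraph after it, the sentence in section 5.3 on de-escalation to levels -1 or -2, and the two MTD sentences. After the change, every possible DLT count at levels -1 and -2 should lead to exactly one decision, and it should be clear which statement governs where two could apply. The clinical content of those decisions is for the sponsor. The cost is a few table rows and some aligned wording in a protocol amendment, with no added patients or procedures.

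### The late CNS-toxicity rule in section 5.4 adds 3 patients at a level that Table 2 may be stopping for the same event, and section 5.9 leaves unclear whether such an event closes the study

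*Combined protocol and SAP*

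**What the plan says.** Section 5.4 contains both enrolment rules.

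- **Table 2.** The text before it says: "Dose escalation will proceed according to the following scheme". With 2 or more DLTs at a level: "Dose escalation will be stopped. This dose level will be declared the maximally administered dose (highest dose administered". With 1 DLT in 3, a second group is entered: "If 1 or more of this group suffer DLT, then dose escalation is stopped, and this dose is declared the maximally administered dose". After either stop, any further patients go one level down: "Three (3) additional patients will be entered at the next lowest dose level if only 3 patients were treated previously at that dose".
- **Delayed CNS events as DLTs.** From more than 30 days after FSRT up to 8 weeks after the last radiation dose, a treatment-related event counts if it meets this definition: "Any grade 3 or 4 adverse event arising within the irradiated volume including but not limited to radiation necrosis or focal neurological deficits".
- **Late rule (text after Table 2).** The trigger is "occurrence of any delayed-onset treatment related grade 3 or higher central nervous toxicity at any time (during and after DLT period of 8 weeks". The consequence is that it "will lead to holding dose-escalation and adding 3 patients to the dose level at which toxicity has occurred". For later events: "Occurrence of additional delayed-onset treatment related grade 3 or higher CNS- toxicity will be reviewed with Protocol Monitoring Committee and IRB".

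Section 5.9 gives two rate thresholds, neurologic death above 14% and symptomatic brain necrosis above 10%, as signs that the combination is too toxic to develop. It then says the same of grade 3 or higher delayed-onset toxicity, without a count or a rate. Discussion and closure of the study come next. Its last sentence sends 'other' treatment-related delayed CNS toxicity of grade 3 or higher to the Protocol Monitoring Committee and the IRB, who decide whether to discontinue.

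**The concern.** One delayed CNS event can trigger both rules in section 5.4, and at a level that Table 2 stops they give opposite instructions about enrolment there. Followed as written, the late rule puts 3 more patients on a dose just stopped for toxicity. Section 5.9 adds a second uncertainty, because part of it can be read as closing the study for an event that section 5.4 answers by enrolling more patients. No section ranks these instructions, so the order would have to be settled while a safety event is being handled. The protocol itself treats delayed toxicity as a main risk: the 8-week wait between levels exists to observe it.

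**Working it through.** The plan gives no figure on this point to reproduce. The check sets the rules side by side.

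**1. Where the rules overlap.** The delayed category starts after day 30 following FSRT, and the DLT window ends at 8 × 7 = 56 days. A treatment-related in-field grade 3 or 4 CNS event on days 31 to 56 is therefore a DLT for Table 2 and also a trigger for the late rule.

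**2. What each rule does with a first such event.**

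| Role of the event at its level | Table 2, further patients there | Late rule, further patients there |
|---|---|---|
| Only DLT in the first 3 | at least 3 | 3 (agree) |
| Second DLT in the first 3 | 0 | 3 (level goes 3 + 3 = 6) |
| DLT in the second group after 1 of 3 | 0 | 3 (level goes 6 + 3 = 9) |

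Example for the second row: one of 3 patients has a non-CNS DLT, and another has grade 3 in-field necrosis on day 40. Table 2 stops the level; the late rule enters 3 there. The earlier DLT is of another type, so the necrosis is the first delayed event, and section 5.4's review step for additional events does not yet apply.

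**3. Can the 3 added patients change the decision?** The Table 2 row for 2 or more DLTs has no denominator. If none of the 3 has a DLT, the counts are 2/6 = 33% or 2/9 = 22%. Both exceed the limit of one in six (17%) in the section 5.3 definition of the MTD. The stop stands whatever happens to them.

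**4. Exposure of the 3 patients (illustration only).** The true DLT rate p at the stopped level is an assumption. Expected DLTs = 3p; chance of at least one = 1 − (1 − p)³.

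| Assumed p | 3p | 1 − (1 − p)³ |
|---|---|---|
| 1/6 | 0.5 | 0.42 |
| 1/3 | 1.0 | 0.70 |
| 1/2 | 1.5 | 0.88 |
| 2/3 | 2.0 | 0.96 |

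The data at a stop say little about p. Exact 95% intervals are 4% to 78% for 2 of 6 and 9% to 99% for 2 of 3, and even these ignore the sequential stopping.

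**5. Section 5.4 against section 5.9.** For a first treatment-related delayed CNS event of grade 3 or higher, section 5.4 gives a hold and 3 more patients; for additional ones it gives review. In section 5.9, the delayed-toxicity sentence followed by the closure sentence gives closure if read literally. Its last sentence gives review for 'other' delayed CNS events but does not say other than what.

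**The case against.** The strongest reply is that the late rule is a single instruction: hold escalation and add 3. A hold presupposes escalation that would otherwise continue. Once Table 2 has stopped it, nothing is left to hold, and enlarging a level that cannot be the MTD serves no dose-finding purpose. The sentence introducing Table 2 also suggests that the table governs. On this reading the late rule only restrains escalation where Table 2 alone would allow it, for instance when a late event follows 0 of 3.

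That is probably the intent, and it largely disposes of one stronger reading. Because follow-up runs 18 months (section 5.7), a reader might infer that an event found long after a level was declared the maximally administered dose must also bring 3 more patients to it. The text does not exclude this, but the word for holding makes it a weak reading.

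The reply does not settle the in-window case. Escalation is still open when the day 31 to 56 event occurs, that one event fires both rules, and the late rule says expressly that it applies during the DLT period.

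A reader might also infer that section 5.9 commits the sponsor to closing the study after one delayed event. The documents do not support that as certain. It would leave the section's last sentence with almost nothing to govern, and closure may belong only to the two rate thresholds.

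Finally, the Protocol Monitoring Committee monitors monthly and may suspend or close the study (section 12.2), so unexamined enrolment at a stopped dose is unlikely. This lowers the practical risk, but it leaves the committee to choose between written rules.

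**Conclusion.** The point holds as a contradiction between stated safety rules, in a narrow situation. When a first delayed in-field grade 3 or 4 event on days 31 to 56 is the DLT that stops a level, the two parts of section 5.4 differ by 3 patients at that level (3 against 0), and those patients cannot alter the Table 2 outcome. With a single DLT in 3 the rules agree.

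Section 5.9 is a separate ambiguity: its literal reading conflicts with section 5.4 and with its own last sentence, and the intent is not certain.

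The conflict follows from the text and needs no assumed event rate. The DLT figures for the 3 added patients do rest on assumed rates and are illustrative. How often the conflict would arise cannot be derived from the documents.

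**What to change.** **Section 5.4:** state that the 3-patient addition applies only where Table 2 has not stopped that level, and that otherwise Table 2 prevails.

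**Section 5.9:** state that closure applies to the neurologic death (>14%) and symptomatic necrosis (>10%) thresholds, which stay in force and still count delayed events. Any other treatment-related delayed-onset CNS toxicity of grade 3 or higher is handled under section 5.4, with Protocol Monitoring Committee and IRB review, which may close the study. Keeping the thresholds explicit matters: a general referral to section 5.4 could move necrosis and neurologic deaths from a rate-based closure rule to discretionary review.

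If the sponsor does intend automatic closure on any such event, delete the 3-patient addition instead.

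The cost is a few sentences of protocol text, with no new visits, data or patients. Extending the hold to the expansion cohort would be a new design choice and is not needed here. The change also does not supply a decision rule for a level of 6 that has not been stopped and grows to 9, a case Table 2 does not cover.
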